	
primary endpoint will be assessed at 3 months after treatment with PNS or standard interventional management.
 
Average pain intensity will be measured for up to 24 months following treatment. Subjects will use numerical rating scales to record average pain intensity (BPI-5) and worst pain intensity (BPI-3) over the past 24 hours, and record daily analgesic medication usage each week at baseline, 1-, 2-, 3-, 6-, 9-, 12-, 18- and 24-months after treatment. The study will compare the efficacy of percutaneous PNS for the treatment of chronic low back pain to standard interventional management for the treatment of chronic low back pain, by evaluating if the treatment effect is equivalent (i.e., statistically non-inferior), and if so, if it is superior.
 
Sites (N)	Up to 30 sites
Subjects (N)	Up to 230 individuals will be randomized
Inclusion Criteria	
 • Age \geq 21 years and \leq 75 years • Able to understand and comply with study requirements and provide written informed consent • Chronic low back pain (i.e., pain lasting longer than 6 months, where the vast majority and center of pain is in the lumbar region, L1-L5 vertebral levels) • Reports an average low back pain score \geq 4 on a scale of 0-10 (BPI-5) • Previous use of at least two types of LBP therapies (e.g., medications, physical therapy, injections, etc.) • At least 4 weeks of stable pain treatment or medication as indicated by subject reported medication history (i.e., no new treatments or change in medication for pain in the last 4 weeks) • Reports active health insurance coverage (e.g., through commercial insurance, Medicare, Medicaid, Tricare)
Exclusion Criteria	
 • Radicular leg pain (e.g., pain that spreads to the lower extremities) or referred pain outside the lumbar region (e.g., sacral pain, hip pain) that is \geq 4 on a scale of 0-10, BPI-5 • Pain in the thoracic or cervical region that is \geq 4 on a scale of 0-10, BPI-5 • Pain from the sacroiliac joint, as determined by the Investigator • Signs of infection on or around the low back, or other conditions that increase risk to the subject in the opinion of the Investigator

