4.2.6. Sample Size & Justification

Up to 30 sites will participate in the study. The study will be planned with a maximum sample size of 230 enrolled subjects

Subjects will be randomized to either Group #1 or Group #2 using a 1:1 randomization scheme.

All subjects who sign a consent will receive a subject ID number. Subjects who sign a consent and do not meet all study eligibility criteria will be considered screen failures and not count against the number of enrolled subjects. Subjects who are randomized at Visit 2 will be counted as enrolled. If a subject does not receive the randomized intervention (e.g., complete PNS or receive a standard interventional procedure), their results may be excluded and/or analyzed separately from the rest of the population.

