Additionally, for subjects in Group 2, another MBB or other diagnostic procedure may be repeated at a repeat Visit 3, if necessary. The necessity of a second Visit 3 will be determined by the Investigator and/or subject's Insurance, as is required for them to receive the randomized therapy (standard interventional management deemed appropriate by the investigator).

If a subject has previously undergone a diagnostic procedure (e.g., MBB, MRI, SCS trial, etc. within 3 months of the baseline visit, results and information may be collected to serve as diagnostic procedures completed for Visit 3.

Details will be collected regarding the approaches used for the diagnostic procedure(s), as well as outcomes following the procedure(s), including adverse events.

Subjects in Group 2 will continue to participate in the study visits independent of their successful completion of diagnostic procedures and/or standard interventional management. For example, if a subject does not proceed to receive lumbar RFA because they failed their MBB (e.g., had less than 50% response), they may receive other treatments for their low back pain recommended by their physician and continue to participate in study visits. In this case, the subject will still return to the clinic at Visit 4 to discuss alternative standard interventional management approaches, which will be regarded as the start of Treatment.

5.4. Visit 4 – Treatment (PNS Lead Placement or start of treatment with Standard Interventional Management)

GROUP 1 - PNS Lead Placement

Subjects randomized to Group 1 will undergo the following prior to lead placement:

- Women of childbearing age and reproductive potential will have a pregnancy test completed as part of eligibility confirmation before or at Visit 4.

- Subjects taking anticoagulants may have their medication adjusted as determined by the Investigator to prevent potential excessive bleeding.

Participants who are randomized to Group 1 and meet all Eligibility criteria will undergo placement of the percutaneous leads. The following measures may be assessed prior to lead placement:

- Selected questions from Brief Pain Inventory (BPI) (e.g., BPI-3, BPI-5)
[REDACTED]
- Current pain treatments/analgesic usage

Figure 2 shows a magnetic resonance image (MRI) of the spine and paraspinal musculature.

[figure not shown]

Figure 2: Magnetic resonance image (MRI) of lumbar paraspinal musculature, multifidus (MF) and longissimus (LS) (54).

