Data regarding the specific details of the lead placement procedure will be collected during this visit and recorded on the appropriate CRF. Images (e.g., photographic, video, ultrasound) may be collected to provide a visual record of the locations of electrodes/leads and anatomy. Subject consent will be obtained for photography or video recording, and subjects will be de-identified in photos or videos.

GROUP 2 - Standard Interventional Management

Subjects in Group 2 will receive standard interventional management for the treatment of their low back pain, as usual, at the discretion of the site investigator. Visit 4 is not required to be completed on the exact day of the intervention; subjects may return for the visit on a separate day.

The following measures will be assessed:

- Selected questions from Brief Pain Inventory (BPI) (e.g., BPI-3, BPI-5)
[REDACTED]
- Current pain treatments/analgesic usage

Details will be collected regarding the approaches used for intervention (e.g., system manufacturer, parameters, location, etc), as well as outcomes following the procedure. Subjects in Group 2 will continue to participate in the study visits independent of their successful completion of diagnostic testing and/or standard interventional management procedure(s) (i.e., even if a subject does not proceed to receive RFA, SCS, or surgery, they may continue to participate in study visits).

It is possible that treatment with standard interventional management may not be completed at this visit (e.g., if multiple nerves and/or levels are to be ablated with RFA during the procedure, or additional treatments or procedures are required). Thus, at the conclusion of this Visit, a subject will proceed to treatment phase. The subject will receive care as usual following the procedure and return for study visits according to the visit schedule. The subject may return as needed to complete additional diagnostic or interventional procedures throughout the study. In this scenario, the subject will still maintain the schedule of visits starting from the first Visit 4.

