Subjects may elect not to undergo a diagnostic procedure and/or treatment (e.g., subject elects to continue their usual care for back pain) but are still willing to remain in the study. In this event, if the subject has not undergone a diagnostic procedure by the end of the Visit 3 window, they will progress directly to Visit 4 (i.e., Visit 3 will be marked as "missed" and Visit 4 will be completed via phone). Regardless of the mode of participation, subjects who continue participation through 12 months after "Start of Treatment" (completion of Visit 16) will be eligible for crossover.

Subjects in Group 2 who receive standard interventional management may be eligible to receive treatment with PNS as part of the study via crossover after 12 months (Visit 16).

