5.6. Visit 12: 8 weeks after Treatment

Visit 12 will occur 8 weeks (2 months) after Visit 4 (Treatment). At this visit, subjects in Group 1 will discontinue use of the stimulation therapy and have leads removed. Percutaneous leads must be removed within 60 days of lead placement for Group 1 subjects. All subjects will be queried for adverse events and lead exit sites will be inspected in Group 1. Additional outcome measures will be administered according to the schedule of procedures (Appendix B).

At this visit, the previous weekly diary will be collected and a new weekly diary will be distributed for daily recording of "average pain" (BPI-5), "worst pain" (BPI-3), and analgesic usage prior to the next visit (Visit 13). If a diary is lost or not returned at the

visit, a diary for that visit may be completed by the patient after the visit and returned (e.g., via mail/email). If a subject is unable to return to the clinic for a visit, options to collect the most important assessments (e.g., pain intensity, ODI) and data (e.g., LBP treatment use, adverse events, etc.) will be made available to the subject (e.g., assessment of surveys and visit questions via phone or video call, remote completion of surveys via mail, email, ePro, etc.).

[figure not shown]
At the conclusion of this visit, Group 1 subjects' leads will be removed by gentle traction

5.7. Follow up Visits: Visits 13 (3 month), Visit 14 (6 months), Visit 15 (9 months), Visit 16 (12 months), Visit 17 (18 months), and Visit 18 (24 months)

Follow up visits will occur at 3, 6, 9, 12, 18, and 24 months (Visits 13-18) after Treatment (Visit 4; See Schedule of Visits in Appendix B). Outcome measures will be administered according to the schedule of procedures (Appendix B).

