8.1. Plan to maximize subject retention and minimize loss of data

Significant efforts will be made to maintain maximum subject retention and follow up data and minimize the percentage of missing data.

Prior experience indicates a potential cause of data loss is when a lead is dislodged or removed before scheduled end of PNS therapy (60 days).

Additional instructions have been provided regarding bandaging to the subjects to minimize the chance of accidental lead dislodgement.

Subject withdrawal from the study is a potential source of data loss. Study investigators and staff will be trained to have clear discussions with subjects considering withdrawing from the study. During the discussions, subjects will be reminded that they may withdraw from the study at any time and investigators will determine if any burdens of continuing in the study can be eased to enable participation at a level that is more amenable to the subject. For example, if subjects indicate a lack of interest in continued participation, they can be offered an opportunity to provide only the most essential and easily collectable data (e.g., recall pain scores and AE questions regarding their safety). To further reduce burden associated with time and travel to the clinical site, subjects can be provided with the option to complete AE questions, surveys, or diaries over the phone or return these via other methods (e.g., a preaddressed, postage-paid envelope, email, ePro, etc).

Subjects in either group may continue to participate in the study visits independent of their successful completion of diagnostic procedures and/or standard interventional management. These subjects may be offered the option to continue with the study and provide only the most essential and easily collectable data (including the option of switching to all telephone calls and completing the most important visits). Subjects also have the option to receive SOC LBP treatments from their regular, outside medical providers (i.e., not exclusively from the study site). If so, these subjects will continue to be followed by the site for research only visits/calls. Alternative options may be utilized to minimize data loss in subjects.

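### Only Group 2 has an explicit start of follow-up for untreated subjects; a randomized Group 1 subject who never receives leads has no stated day zero for the 3-month endpoint

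*Protocol*

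**What the plan says.** Section 5.7 sets the clock for both arms: "Follow up visits will occur at 3, 6, 9, 12, 18, and 24 months (Visits 13-18) after Treatment (Visit 4"). The primary endpoint (section 4.3.1.1) uses the diary for the week before Visit 13. That diary is handed out at Visit 12, which is itself timed from Visit 4 (section 5.6).

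Group 2 has three provisions for subjects who go untreated:

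- After a failed block, the subject attends Visit 4 to discuss alternatives, and that visit counts as the start of treatment (section 5.3).
- Without a diagnostic procedure, "if the subject has not undergone a diagnostic procedure by the end of the Visit 3 window, they will progress directly to Visit 4", done by phone (section 5.4, Group 2).
- In general, "even if a subject does not proceed to receive RFA, SCS, or surgery, they may continue to participate in study visits" (section 5.4, Group 2).

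For Group 1, section 5.4 says "Participants who are randomized to Group 1 and meet all Eligibility criteria will undergo placement of the percutaneous leads", and Table 1 (section 5.10) names the Group 1 Visit 4 as lead placement and programming. Pregnancy is a Group 1-only exclusion checked before treatment starts (section 4.2.1), hence possibly after randomization at Visit 2.

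Section 8.1 adds a retention rule: "Subjects in either group may continue to participate in the study visits independent of their successful completion of diagnostic procedures and/or standard interventional management". It also repeats the phone Visit 4 rule without naming a group.

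On status, sections 4.2.6 and 7.5 count everyone randomized as enrolled. Section 7.4 classes any consented subject who does not go on to treatment procedures as a screen failure.

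**The concern.** The comparison is of success proportions in randomized groups, so the 3-month outcome should be sought in the same way from every randomized subject. The explicit rules do that for untreated controls. They do not do it for a Group 1 subject who had the block, or whose earlier block was accepted, and then declined or could not receive leads.

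If such subjects drop out of data collection and would have responded less often than implanted subjects, the observed PNS proportion is too high. That direction favours both the non-inferiority test and the superiority test that follows it. The collection rule belongs in the protocol: an analysis plan can impute or reclassify, but it cannot observe a diary that was never issued.

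**Working it through.** The protocol states no figure that depends on this point, so there is nothing to reproduce. The check is a reading of the rules, followed by an illustration.

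**Step 1: trace each untreated subject to a Visit 4.**

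| Randomized subject | Stated Visit 4 | Source |
|---|---|---|
| Group 2, failed block, no RFA | Clinic discussion, counted as start of treatment | 5.3 |
| Group 2, no diagnostic procedure | Phone call | 5.4, 8.1 |
| Group 1, no diagnostic procedure | Phone call, if 8.1 is read as covering both groups | 8.1 |
| Group 1, first leads placed, further leads declined | Date of the first lead placement | 5.9 |
| Group 1, block done, leads never placed | None stated | – |

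**Step 2: test the provisions that might fill the last row.**

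- The either-group sentence in 8.1 lists diagnostic procedures and standard interventional management, not lead placement. It permits visits to continue but sets no date from which to count them.
- The phone rule in 8.1 opens with subjects who forgo a diagnostic procedure and/or treatment, but its trigger is a missed diagnostic procedure. A subject who had the block does not meet it. The passage ends with eligibility for crossover, which section 5.12 gives to Group 2.
- Section 5.12 keeps Group 1 subjects who also seek other treatments on the normal schedule, but gives no starting date to someone never implanted.
- Section 7.4 points the other way by making the subject a screen failure, against 4.2.6 and 7.5.

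**Step 3: illustrate the size.** From the protocol: "Up to 230 individuals will be randomized", allocated 1:1, so 230 / 2 = 115 per arm at the maximum. Assumed, because the protocol gives no such rates: a share u of 5–15% of Group 1 never implanted and unobserved, success p = 50% if implanted, and success q = 10–20% if not.

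Number affected: 115 × 0.05 = 5.75 to 115 × 0.15 = 17.25, about 6 to 17 subjects.

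The observed proportion is p. The proportion in all randomized subjects is (1 − u)p + uq. The difference is u(p − q):

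- Low: 0.05 × (0.50 − 0.20) = 0.015, or 1.5 points
- Middle: 0.10 × (0.50 − 0.20) = 0.030, or 3 points
- High: 0.15 × (0.50 − 0.10) = 0.060, or 6 points

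Widening p to 50–60% and q to 10–30% gives 0.05 × (0.50 − 0.30) = 1.0 point up to 0.15 × (0.60 − 0.10) = 7.5 points.

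**Step 4: set this against the sampling error.** With 50% success in both arms, SE = √(2 × 0.25 / 115) = 0.0659. If 15% of Group 1 is lost, SE = √(0.25 / 97.75 + 0.25 / 115) = 0.0688. Under an assumed one-sided 2.5% test with SE 0.0659, the error becomes 1 − Φ(1.96 − bias / 0.0659):

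| Bias (points) | Error |
|---|---|
| 1.5 | 4.2% |
| 3 | 6.6% |
| 6 | 14.7% |

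These error figures are rough. They keep 115 per arm despite the loss, and they set equal rates although the rates differ by the margin at the non-inferiority boundary.

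**Step 5: see how far the direction depends on the analysis.** If the unobserved subjects were counted as failures, the Group 1 proportion would be (1− u)p and the bias −uq: from −0.05 × 0.10 = −0.5 points to −0.15 × 0.20 = −3 points. The sign reverses.

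**The case against.** A reader might infer that the 3-month outcome is never scheduled for an untreated Group 1 subject, and that follow-up is lost in one arm only. The documents do not support either statement.

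- Section 8.1 lets subjects in either group continue visits, offers telephone-only participation and collection of essential data only, and allows recall scores in place of a missing diary. Its phone rule mentions treatment as well as diagnostic procedures and names no group. The intent to keep collecting pain scores in both arms is plain, and a site could act on it.
- Section 4.2.4 (Subject Disposition), the window column of Table 1 and Appendices B.1–B.3 cannot be read in the public copy. Any of them may hold the missing rule, so its absence cannot be asserted.
- The detailed Group 2 rules have a reason. Controls face diagnostic and insurance hurdles, while Group 1 proceeds after one block whatever its result (section 5.3). Never-implanted Group 1 subjects may be few.
- The inflation presumes that untreated controls stay in the analysis and unobserved PNS subjects do not. Section 4.2.6 allows exclusion or separate analysis in either arm, and section 8.1 foresees imputation. The analysis plan may settle both.

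All of this stands, and it limits the point to an ambiguity with an arm-specific consequence. It does not remove the ambiguity: the readable text sets no day zero for this subject, and permission to continue is not a schedule. Nor does it resolve the conflict between section 7.4 and sections 4.2.6 and 7.5.

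**Conclusion.** The point holds in a limited form. The readable protocol gives an explicit substitute start of follow-up to Group 2, but not to a Group 1 subject who had the block and was never implanted, and it contradicts itself on whether that subject is enrolled or a screen failure. Outcome collection can therefore differ by arm, and may overstate PNS success.

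The 1.5–6 points are an illustration resting wholly on the assumed share and response rates. The error figures also assume a 2.5% one-sided test and an analysis that drops the unobserved PNS subjects while keeping untreated controls. No non-implantation rate, response rate, alpha or margin is readable, so no actual bias is shown. The conclusion also depends on the unreadable sections not already covering the case. This is a cheap improvement worth making, not a demonstrated flaw in the result.

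**What to change.** If the unreadable sections do not already do so:

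1. In section 5.4 (Group 1) and section 8.1, state that a randomized Group 1 subject without lead placement by the end of the Visit 4 window has Visit 4 completed by phone, that this is day zero, and that the follow-up schedule is kept, including the 3-month diary.
2. In the either-group sentence of section 8.1, add PNS lead placement to the procedures whose completion is not a condition for staying in study visits.
3. Reconcile section 7.4 with sections 4.2.6 and 7.5 so that no randomized subject is reclassified as a screen failure.

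The cost is a few sentences and phone follow-up of a small number of subjects. No clinical procedure changes. The observed PNS success proportion may come out somewhat lower.

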5.5. Visits 5-11: Weeks 1 through 7 after Treatment

During the early phase of visits after Visit 4 (PNS lead placement or standard intervention), follow-up visits will take place weekly, either in person or over the phone, and will occur as follows:

Visit	GROUP 1		GROUP 2	
	In Clinic	Telephone	In Clinic	Telephone
Visit 5 (1 week)	X			X
Visit 6 (2 weeks)	X			X
Visit 7 (3 weeks)		X		X
Visit 8 (4 weeks /1 month)	X		X	
Visit 9 (5 weeks)		X		X
Visit 10 (6 weeks)	X			X
Visit 11 (7 weeks)		X		X

During these visits, all subjects will be queried for study-related adverse events and lead exit sites will be inspected in Group 1. Outcome measures will be administered according to the schedule of procedures (Appendix B).

At Visit 4 and Visit 8 weekly diaries will be distributed for daily recording of "average pain" (BPI-5), "worst pain" (BPI-3), and analgesic usage prior to the next in clinic visit and to be turned in at that time (e.g., Visit 8 or Visit 12). If a diary is lost or not returned at the visit, a diary for that visit may be completed by the patient after the visit and returned (e.g., via mail/email). Adjustment of stimulation parameters may be performed for Group 1, as determined by the site staff.

If necessary (e.g., to minimize missing data or encourage subject compliance), study staff may make arrangements to reduce burden of study participation on a subject. If a subject is unable to return to the clinic for a visit, options to collect the most important assessments (e.g., pain intensity, ODI) and data (e.g., LBP treatment use, adverse events, etc.) will be made available to the subject (e.g., assessment of surveys and visit questions via phone or video call, remote completion of surveys via mail, email, ePro, etc.).

5.6. Visit 12: 8 weeks after Treatment

Visit 12 will occur 8 weeks (2 months) after Visit 4 (Treatment). At this visit, subjects in Group 1 will discontinue use of the stimulation therapy and have leads removed. Percutaneous leads must be removed within 60 days of lead placement for Group 1 subjects. All subjects will be queried for adverse events and lead exit sites will be inspected in Group 1. Additional outcome measures will be administered according to the schedule of procedures (Appendix B).

At this visit, the previous weekly diary will be collected and a new weekly diary will be distributed for daily recording of "average pain" (BPI-5), "worst pain" (BPI-3), and analgesic usage prior to the next visit (Visit 13). If a diary is lost or not returned at the

visit, a diary for that visit may be completed by the patient after the visit and returned (e.g., via mail/email). If a subject is unable to return to the clinic for a visit, options to collect the most important assessments (e.g., pain intensity, ODI) and data (e.g., LBP treatment use, adverse events, etc.) will be made available to the subject (e.g., assessment of surveys and visit questions via phone or video call, remote completion of surveys via mail, email, ePro, etc.).

[figure not shown]
At the conclusion of this visit, Group 1 subjects' leads will be removed by gentle traction

5.7. Follow up Visits: Visits 13 (3 month), Visit 14 (6 months), Visit 15 (9 months), Visit 16 (12 months), Visit 17 (18 months), and Visit 18 (24 months)

Follow up visits will occur at 3, 6, 9, 12, 18, and 24 months (Visits 13-18) after Treatment (Visit 4; See Schedule of Visits in Appendix B). Outcome measures will be administered according to the schedule of procedures (Appendix B).

In accordance with the Schedule of Visits (Appendix B), diaries will be collected at each follow up visit. If a diary is lost or not returned at the visit, a diary for that visit may be completed by the patient after the visit and returned (e.g., via mail/email). Diaries for the next visit will be distributed, for daily recording of baseline "average pain" (BPI-5), "worst pain" (BPI-3), and analgesic usage for the week prior to the next visit. Alternatively, the diary may be mailed/mailed to the subject for completion prior to the next visit. To mitigate missing data, an unreturned diary may be replaced with weekly recall "average pain" (BPI-5), "worst pain" (BPI-3) from that visit. If the subject is unable to return to the clinic, the diary and questionnaires may be completed and returned via mail, or the information can be collected by the research staff in a telephone call. Further, if a subject is unable to return to the clinic for a visit, options to collect the most important assessments (e.g., pain intensity, ODI) and data (e.g., LBP treatment use, adverse events, etc.) will be made available to the subject (e.g., assessment of surveys and visit questions via phone or video call, remote completion of surveys via mail, email, ePro, etc.).

In addition, subjects will be queried for adverse events. If no ADEs are noted, the subject will be discharged from the study at the site following the 24-month visit. Any ADE will be documented, addressed, and followed to resolution.

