4.3.1. Primary Endpoints

4.3.1.1. Primary Efficacy Endpoint

The primary outcome of this study will be calculated as the mean score of average daily back pain intensity 3 months after start of treatment to baseline. This will be recorded using Question 5 of the Brief Pain Inventory Short Form (BPI-5; details of BPI below), which assesses “average pain” on an 11-point numerical rating scale, with one end

representing “no pain” (0) and the other end representing “pain as bad as you can imagine” (10). Subjects will record BPI-5 scores daily in a diary, and the mean score for each week will be calculated for each subject. The primary endpoint will be a highly clinically significant reduction in back pain evidenced by $\geq 50\%$ reduction in mean “average pain” (BPI-5) over the week prior to the 3-month follow-up visit (Visit 13) compared to baseline.

The primary endpoint compares the proportion of subjects in Group 1 (PNS) relative to that in Group 2 (standard interventional management) that achieve $\geq 50\%$ reduction in average back pain intensity from baseline to 3-months after start of treatment. This endpoint will examine the statistical non-inferiority of the proportion of clinical successes in Group 1 compared to Group 2, and if non-inferiority is achieved, examine the statistical superiority of the proportion of successes in Group 1 compared to Group 2.

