Subjects may elect not to undergo a diagnostic procedure and/or treatment (e.g., subject elects to continue their usual care for back pain) but are still willing to remain in the study. In this event, if the subject has not undergone a diagnostic procedure by the end of the Visit 3 window, they will progress directly to Visit 4 (i.e., Visit 3 will be marked as "missed" and Visit 4 will be completed via phone). Regardless of the mode of participation, subjects

who continue participation through 12 months after "Start of Treatment" (completion of Visit 16) will be eligible for crossover.

Subjects are offered compensation for each visit as it is completed, including unscheduled visits, even if they do not complete all the visits. This compensation is intended to cover costs associated with taking the time to participate in the study. [REDACTED]

A potential source of data loss is the failure of the subjects to return their completed diaries. Thus, subjects may receive reminder calls from the clinical study staff before certain visits to remind them to bring their completed diaries with them to the visit. For long-term follow up visits, subjects may complete a diary after a visit and return via mail/email if the original diary for that visit was lost or was not completed. Diaries may also be completed electronically.

If a subject is unable to return any follow-up diary, the data may be replaced using the one-week recall data (question #3 or #5 of the validated BPI-SF). If the subject later returns the diary, the diary data will be used over the one-week recall data. If a subject is unable to return to the clinic for a visit, options to collect the most important assessments (e.g., pain intensity, ODI) and data (e.g., LBP treatment use, adverse events, etc.) will be made available to the subject (e.g., assessment of surveys and visit questions via phone or video call, remote completion of surveys via mail, email, ePro, etc.). These options will mitigate the problem of missing data and minimize the need to impute scores. Scores will only be imputed if recall (or remotely collected) data are unavailable and cannot be obtained.

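### Should a diary filled in after Visit 13 be barred from replacing the recall score taken at that visit?

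*Protocol*

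**What the plan says.** Section 4.3.1.1 has subjects rate average pain (BPI-5) daily in a diary. Success is a reduction of at least 50% in the mean "over the week prior to the 3-month follow-up visit (Visit 13) compared to baseline". The synopsis says only that the score is the average of a weekly diary at 3 months, and that ratings refer to the past 24 hours.

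Section 5.6 hands out the Visit 13 diary at Visit 12. Section 5.7, whose heading includes Visit 13, describes follow-up diaries as recording pain and "analgesic usage for the week prior to the next visit". It also says, as 5.5 and 5.6 do for earlier visits, that if a diary is lost or not returned, "a diary for that visit may be completed by the patient after the visit and returned". It then allows weekly recall from the visit to stand in for an unreturned diary.

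Section 8.1 adds three rules:
- In long-term follow-up, the patient is permitted to "complete a diary after a visit and return via mail/email if the original diary for that visit was lost or was not completed".
- "If a subject is unable to return any follow-up diary, the data may be replaced using the one-week recall data". The next sentence reads: "If the subject later returns the diary, the diary data will be used over the one-week recall data".
- "Scores will only be imputed if recall (or remotely collected) data are unavailable and cannot be obtained".

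**The concern.** The endpoint is tied to one week, while the collection rules speak of completing a diary after that week, not merely returning it. Because each rating covers 24 hours, such a diary either rates days after Visit 13 or is filled in from memory. Neither is a daily rating in the defined week. If the 8.1 preference reaches these diaries, one of them could displace a recall score that does cover that week.

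The point touches the primary endpoint, in a comparison where subjects know what treatment they received. Other treatment is allowed during follow-up (sections 5.4 and 5.12), so days after the visit may differ from the days before it. The baseline half of the same percentage change is held to a strict standard: section 5.2 requires all 7 diary days before randomization. And because the protocol itself fixes both the week and the order of sources, the matter cannot simply be called one for the SAP.

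**Working it through.** **What the texts require, side by side**

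1. Week: the 7 days before Visit 13 (4.3.1.1).
2. Completion after the visit: allowed (5.7 and 8.1). The visible text does not say which days the diary must cover or by when it must be complete. The window column of Table 1 and Appendix B are not shown, so a limit may exist there.
3. Order of sources: the preference sentence in 8.1 directly follows the sentence on a subject who cannot return a diary. It speaks of that diary coming back later, which is naturally the original. No sentence expressly ranks a diary begun after the visit above recall; that ranking appears only when two separate sentences of 8.1 are joined.
4. Recall: 5.7 allows it for any unreturned diary, but with *may*. Section 4.3.2 likewise says that individual BPI items *may* be assessed at visits. A Visit 13 recall score is therefore likely but not assured.

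The mismatch between 1 and 2 is real but narrow. The supposed conflict in 3 rests on the less natural reading.

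**Scale**

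The visible protocol gives no margin, alpha, power or response rates, so there is no design figure to reproduce. With at most 230 subjects allocated 1:1 there are 230/2 = 115 per group. One changed responder moves a group's proportion by 1/115 = 0.87 points. As an example with assumed scores, a baseline mean of 6.0 puts the cut at 3.0, so 3.2 is a failure and 2.9 a success.

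**Would recall do better than a late diary?**

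All inputs here are assumptions:
- Baseline is N(6, 1.3), kept within 4 to 10.
- The 3-month mean is N(0.55 × baseline, SD 2) in one arm and N(0.62 × baseline, SD 2) in the other, clipped to 0 to 10.
- A late diary is the true mean plus a shift plus N(0, SD) error, rounded to sevenths.
- Recall has the same shift and error but is rounded to a whole number.
- Success is follow-up ≤ 0.5 × baseline. This gives 44.7% and 36.3%, a true gap of 8.39 points.

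Percent of substituted subjects whose status changes, with no shift:

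| Error SD | Late diary | Recall |
|---|---|---|
| 0.5 | 7.7 | 8.8 |
| 0.8 | 12.0 | 12.7 |
| 1.0 | 14.6 | 15.2 |

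Effect of a shift at error SD 0.8. The second and third columns give the change in success, in points, among substituted subjects. The last two give the group gap when 20% of both arms are substituted:

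| Shift | Late diary | Recall | Gap, late diary | Gap, recall |
|---|---|---|---|---|
| -0.5 | +9.6 | +9.8 | 8.31 | 8.30 |
| 0 | +0.4 | +0.6 | 8.27 | 8.26 |
| +0.5 | -8.6 | -8.3 | 8.16 | 8.15 |

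Over a whole arm the late-diary effect is share × change among those substituted:
- 5%: 0.05 × 9.6 = +0.5 or 0.05 × (-8.6) = -0.4 points
- 10%: +1.0 or -0.9 points
- 20%: +1.9 or -1.7 points

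At 20% that is 23 of 115 subjects, and 23 × 0.096 ≈ 2 changed responders. It would carry over to the group difference in full only if late diaries, with that shift, were confined to one arm.

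**The case for a change.** The strongest case for a change is that the text says completed, not returned, after the visit, and that 8.1 attaches no condition on entry dates to its preference. One clause in each of 5.7 and 8.1 would settle the meaning, cost little, and keep the priority of a diary kept on time. The simulation does not answer this, because the argument is about consistency with the defined week and not about accuracy. It also gives late diaries and recall the same shift, and nothing in the document shows that their shifts would be equal.

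Part of this stands: the visible wording does not say which days a replacement diary covers, and a clarifying phrase would do no harm. Three things limit it.

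- Putting recall first gives up something. Baseline is a 7-day diary mean, so a diary at 3 months keeps the same instrument on both sides of the percentage change, whereas recall sets a single item against that mean.
- Allowing a short window after the visit would readmit entries from outside the week, which is the complaint itself. Insisting on day-by-day entry is hard to verify with a paper diary.
- Recording the source of each score, tabulating sources by group and repeating the analysis with in-window diaries are ordinary SAP content. The SAP is not at hand, so their absence here shows nothing.

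The open comparison is a fair reason for care, but it applies to recall as much as to a diary. The leads are percutaneous and come out at Visit 12, so they are no longer in place in the assessment week.

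**Conclusion.** No change to the plan is needed. There is a small gap in wording between the endpoint week in 4.3.1.1 and the diary rules in 5.7 and 8.1. Analysts can fill it sensibly by preferring an original diary kept in the week and returned late, using recall where no such diary exists, and imputing last. That is also the natural reading of 8.1. For diaries really completed after the visit, either choice is a fair trade-off between the same instrument and the right week.

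No bias between arms and no gain in accuracy from a change has been shown. Under equal assumed error and shift, the two sources give group gaps within 0.01 points of each other at 20% use in both arms. These figures rest wholly on assumed distributions and on equal behaviour of the two sources. The frequency of late diaries is unknown, and any limit in the unseen Table 1 windows or Appendix B would narrow the point further.
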